5.2 SAFETY ANALYSIS SET

The Safety Analysis Set (SAF) refers to all patients with at least one treatment intake documented (i.e. date of first intake available), whatever the treatment (Sunitinib or Axitinib).

5.3 OTHER ANALYSIS SET

Not Applicable

5.4 SUBGROUPS

Type of 2nd line treatment post SU:

o SU - AXI subgroup

It refers to all patients from the FAS receiving the combined SU-AXI sequence during the observation period. It includes

- patients enrolled at AXI initiation in 2nd line post SU treatment ("SU (retrospective) - AXI")
- and patients enrolled at SU initiation with SU prospective part and receiving AXI in 2nd-line post SU ("SU (prospective)-AXI") (AXI declared as 2nd line at SU discontinuation)

Two different baselines will be considered in the analyses of this subgroup: AXI initiation to explore only the AXI treatment period and SU initiation to consider the SU – AXI sequence.

6 ENDPOINTS AND COVARIATES

6.1 EFFICACY/EFFECTIVENESS ENDPOINT(S)

6.1.1 Primary Endpoints

- Progression Free Survival (PFS) under Axitinib in 2nd line post Sunitinib

The PFS will be defined as the time from when the patient receives the first dose of AXI to the time of progression or death due to any cause, whichever occurs first.

PFS status and PFS time will be calculated as detailed below:

Variable name	Definition
PFS status	Patient will not be censored for the PFS analysis (PFS status = 1) in the following cases:
	 Tumor Assessment showing PD in at least one Axitinib follow-up visit (cf. CRF page 29)
	 Death within 3 months after treatment discontinuation / last Tumor Assessment. Death could be reported whether on Axitinib discontinuation page (cf. CRF page 35) or on Study Discontinuation visit (cf. CRF page 37)
	In all other cases, patient will be censored for the PFS analysis (PFS status $= 0$).
	Note: the following cases should be discussed at time of DRMs:
	- Patients with a PD not documented through a Tumor Assessment
	- Patients with no regular Tumor Assessments (i.e. not every 3/4 months)
PFS time	The time to disease progression will be calculated in months as:
(months)	 (Date of first Tumor Assessment showing PD in at least one Axitinib follow-up visit - Start date of Axitinib + 1) / 30.44, if case n°1 described above is reported
	 (Date of death - Start date of Axitinib + 1) / 30.44, if case n°2 described above is reported
	Else, the time to disease progression will be censored as follows:

Variable name	Definition
	 (Date of Axitinib discontinuation - Start date of Axitinib + 1) / 30.44 if patient discontinued Axitinib for any reason other than PD
	 (Date of last follow-up visit - Start date of Axitinib + 1) / 30.44 if patient is lost to follow-up or still under Axitinib
	Note; this could be adapted if necessary (to be discussed at time of DRMs)
	Note:
	- Start date of Axitinib will be the one reported at time of Axitinib initiation visit (cf. CRF page 25 "Therapy started with Axitinib in 2nd line on")
	- Axitinib discontinuation date will be the Date of progression/intolerability or death reported at time of Axitinib discontinuation (cf. CRF page 35)

- Progression Free Survival (PFS) for the sequence Sunitinib-Axitinib

The PFS will be defined as the time from when the patient receives the first dose of SU in 1st line, until progression or death due to any cause with the 2nd- line treatment considered in the analysis, whichever occurs first.

PFS status and PFS time will be calculated as detailed below:

Variable name	Definition
PFS status	Patient will not be censored for the PFS analysis (PFS status = 1) in the following cases:
	1) Tumor Assessment showing PD in at least one Axitinib follow-up visit (cf. CRF page 29)
	 Death within 3 months after treatment discontinuation / last Tumor Assessment. Death could be reported whether on Axitinib discontinuation page (cf. CRF page 35) or on Study Discontinuation visit (cf. CRF page 37)
	In all other cases, patient will be censored for the PFS analysis (PFS status $= 0$).
	Note: the following cases should be discussed at time of DRMs:

PFIZER CONFIDENTIAL

Page 10 of 41

Variable name	Definition
	- Patients with a PD not documented through a Tumor Assessment
	- Patients with no regular Tumor Assessments (i.e. not every 3/4 months)
PFS time	The time to disease progression will be calculated in months as:
(months)	 (Date of first Tumor Assessment showing PD in at least one Axitinib follow-up visit - Start date of Sunitinib + 1) / 30.44, if case n°1 described above is reported
	 (Date of death - Start date of Sunitinib + 1) / 30.44, if case n°2 described above is reported
	Else, the time to disease progression will be censored as follows:
	 (Date of Axitinib discontinuation - Start date of Sunitinib + 1) / 30.44 if patient discontinued Axitinib for any reason other than PD
	• (Date of last follow-up visit - Start date of Sunitinib + 1) / 30.44 if patient is lost to follow-up or still under Axitinib
	Note; this could be adapted if necessary (to be discussed at time of DRMs)
	Note:
	- Start date of Sunitinib will be the one reported :
	- at time of Sunitinib initiation visit for patients enrolled at SU initiation (cf. CRF page 11 "Therapy started with Sunitinib in 1st line on")
	- at time of Axitinib initiation visit for patients enrolled at AXI initiation (cf. CRF page 26 "Therapy started with Sunitinib in 1st line on")
	- Axitinib discontinuation date will be the Date of progression/intolerability or death reported at time of Axitinib discontinuation (cf. CRF page 35)

- Time to Treatment Failure (TTF) under Axitinib in 2nd line post Sunitinib

The TTF will be defined as the time from when the patient receives the first dose of AXI to the date of AXI discontinuation (date completed by the physician), whatever the reason for discontinuation and whatever the following therapeutic strategy.

Variable name	Definition
TTF status	Patient will not be censored for the TTF analysis (TTF status = 1) in the following cases:
	 Axitinib discontinued due to Progression, Intolerability or Death (cf. CRF page 35)
	 Study Discontinuation for any reason except lost to follow-up or patient's request whereas last treatment received is Axitinib (cf. CRF page 37)
	In all other cases, patient will be censored for the TTF analysis (TTF status = 0).
	Note: Other reasons for Axitinib discontinuation as well as other reason for study discontinuation (whereas last treatment received is Axitinib) will be reviewed at time of DRMs in order to decide whether corresponding cases should be censored or not for TTF analysis
TTF time	The time to treatment failure will be calculated in months as:
(months)	• (Date of progression/intolerability or death reported at time of Axitinib discontinuation - Start date of Axitinib + 1) / 30.44, if case n°1 described above is reported
	 (Date of death reported on the Study Discontinuation form - Start date of Axitinib + 1) / 30.44, if case n°2 described above is reported and reason for study discontinuation is 'death'
	• (Axitinib end date reported on the Study Discontinuation form - Start date of Axitinib + 1) / 30.44, if case n°2 described above is reported and reason for study discontinuation is not 'death' and Axitinib status at last visit is 'discontinued'
	Note: as only month and year of Axitinib end are reported in such cases, day of Axitinib end will automatically be "forced" to 01
	• (Last visit date reported on the Study Discontinuation form - Start date of Axitinib + 1) / 30.44, if case n°2 described above is reported and reason for study discontinuation is not 'death' and Axitinib status at last visit is 'ongoing'
	• (Minimum of {Date of progression/intolerability or death reported at time of Axitinib discontinuation ; Date of death reported on the Study Discontinuation form ; Axitinib end date reported on the Study Discontinuation form ; Last visit date reported on the Study

TTF status and TTF time will be calculated as detailed below:

PFIZER CONFIDENTIAL

Page 12 of 41

Variable name	Definition
	Discontinuation form} - Start date of Axitinib + 1) / 30.44 , if more than 1 case described above is reported
	Else, the time to treatment failure will be censored as follows:
	• (Maximum of { Date of last Axitinib follow-up visit ; Last visit date reported on the Study Discontinuation form whereas last treatment received is Axitinib } - Start date of Axitinib + 1)/30.44
	Note : Start date of Axitinib will be the one reported at time of Axitinib initiation visit (cf. CRF page 25 " Therapy started with Axitinib in 2nd line on ")

- Time to Treatment Failure (TTF) for the sequence Sunitinib-Axitinib

The TTF will be defined as the time when the patient receives the first dose with SU in 1st line to the time of AXI 2nd line treatment discontinuation (date completed by the physician), whatever the reason for discontinuation and whatever the following therapeutic strategy.

Variable name	Definition
TTF status	Patient will not be censored for the TTF analysis (TTF status = 1) in the following cases:
	 Axitinib discontinued due to Progression, Intolerability or Death (cf. CRF page 35)
	 Study Discontinuation for any reason except lost to follow-up or patient's request whereas last treatment received is Axitinib (cf. CRF page 37)
	In all other cases, patient will be censored for the TTF analysis (TTF status = 0).
	Note: Other reasons for Axitinib discontinuation as well as other reason for study discontinuation (whereas last treatment received is Axitinib) will be reviewed at time of DRMs in order to decide whether corresponding cases should be censored or not for TTF analysis

TTF status and TTF time will be calculated as detailed below:

Variable name	Definition
TTF time	The time to treatment failure will be calculated in months as:
(months)	• (Date of progression/intolerability or death reported at time of Axitinib discontinuation - Start date of Sunitinib + 1) / 30.44, if case n°1 described above is reported
	• (Date of death reported on the Study Discontinuation form - Start date of Sunitinib + 1) / 30.44, if case n°2 described above is reported and reason for study discontinuation is 'death'
	• (Axitinib end date reported on the Study Discontinuation form - Start date of Sunitinib + 1) / 30.44, if case n°2 described above is reported and reason for study discontinuation is not 'death' and Axitinib status at last visit is 'discontinued'
	Note: as only month and year of Axitinib end are reported in such cases, day of Axitinib end will automatically be "forced" to 01
	• (Last visit date reported on the Study Discontinuation form - Start date of Sunitinib + 1) / 30.44, if case n°2 described above is reported and reason for study discontinuation is not 'death' and Axitinib status at last visit is 'ongoing'
	 (Minimum of {Date of progression/intolerability or death reported at time of Axitinib discontinuation ; Date of death reported on the Study Discontinuation form ; Axitinib end date reported on the Study Discontinuation form ; Last visit date reported on the Study Discontinuation form} - Start date of Sunitinib + 1) / 30.44, if more than 1 case described above is reported
	Else, the time to treatment failure will be censored as follows:
	 (Maximum of { Date of last Axitinib follow-up visit ; Last visit date reported on the Study Discontinuation form whereas last treatment received is Axitinib } - Start date of Sunitinib + 1) / 30.44
	Note: Start date of Sunitinib will be the one reported:
	- at time of Sunitinib initiation visit for patients enrolled at SU initiation (cf. CRF page 11 "Therapy started with Sunitinib in 1st line on")
	- at time of Axitinib initiation visit for patients enrolled at AXI initiation (cf. CRF page 26 "Therapy started with Sunitinib in 1st line on")

6.1.2 Secondary Endpoints

- Time to Strategy Failure (TSF) for the sequence Sunitinib-Axitinib

The TSF will be defined as the time from when the patient receives the first dose with SU in first line to the time of AXI 2nd line treatment discontinuation (date completed by the physician) without the time between discontinuation of SU and start of the 2nd line AXI treatment.

TSF status will be the same as TTF status for the sequence Sunitinib-Axitinib.

TSF time will be equal to:

- For patients enrolled at SU initiation : TTF time (Start date of Axitinib reported at time of Axitinib initiation visit Date of progression/intolerability/death reported at time of Sunitinib discontinuation)
- For patients enrolled at AXI initiation : TTF time (Start date of Axitinib reported at time of Axitinib initiation visit Date of Sunitinib end reported at time of Axitinib initiation visit*)

*cf. CRF page 26 "Therapy with Sunitinib in first line; therapy discontinuation on"

- Overall Survival (OS) for the sequence Sunitinib-Axitinib

The OS will be defined as the time from date of first SU dose to the date of death of any cause. For patients not experiencing the event, their survival times will be censored at the last date they are known to be alive

Variable name	Definition
OS status	Patient will not be censored for the OS analysis (OS status = 1) in the following cases:
	1) Axitinib discontinued due to Death (cf. CRF page 35)
	2) Death reported in Long term Follow-up (cf. CRF page 36)
	 Death reported on the Study Discontinuation form (cf. CRF page 37)
	In all other cases, patient will be censored for the OS analysis (OS status $= 0$).

OS status and OS time will be calculated as detailed below:

Variable name	Definition					
OS time	The overall survival time will be calculated in months as:					
(months)	 (Date of death reported at time of Axitinib discontinuation - Start date of Sunitinib + 1) / 30.44, if case n°1 described above is reported 					
	 (Date of death reported in Long term Follow-up - Start date of Sunitinib + 1) / 30.44, if case n°2 described above is reported 					
	 (Date of death reported on the Study Discontinuation form - Start date of Sunitinib + 1) / 30.44, if case n°3 described above is reported 					
	Else, the overall survival time will be censored as follows:					
	 (Maximum of {All visits dates reported} - Start date of Sunitinib + 1) / 30.44 					
	Note: Start date of Sunitinib will be the one reported:					
	- at time of Sunitinib initiation visit for patients enrolled at SU initiation (cf. CRF page 11 " Therapy started with Sunitinib in 1st line on ")					
	- at time of Axitinib initiation visit for patients enrolled at AXI initiation (cf. CRF page 26 "Therapy started with Sunitinib in 1st line on")					

- Best Response under Axitinib in 2nd line post Sunitinib

Number and percentages of patients by best response (CR, PR, SD or PD) will be presented.

- Objective Response Rate (ORR) under Axitinib in 2nd line post Sunitinib

ORR is defined as the percentage of patients with complete response (CR) or partial response (PR) according to RECIST from the start to the end of Axitinib treatment (cf. CRF page 29).

Patients who die, progress, or drop out for any reason prior to reaching a CR or PR will be counted as non-responders in the assessment of ORR.

All assessments following an assessment of PD will be excluded from the derivation of ORR.

- Clinical benefice Rate (CBR) under Axitinib in 2nd line post Sunitinib

The Clinical Benefit Rate (CBR) will be the proportion of patients with a CR, PR or Stable Disease according to RECIST criteria from the start to the end of Axitinib treatment (cf. CRF page 29).

PFIZER CONFIDENTIAL

Page 16 of 41

Patients who die, progress, or drop out for any reason prior to reaching a CR, PR or SD will be counted as non-responders in the assessment of CBR.

All assessments following an assessment of PD will be excluded from the derivation of CBR.

- Objective Response Rate (ORR) under TKI in 2nd line post Sunitinib

ORR is defined as the percentage of patients with complete response (CR) or partial response (PR) as best response under TKI treatment (cf. CRF page 36).

- Clinical benefice Rate (CBR) under TKI in 2nd line post Sunitinib

The Clinical Benefit Rate (CBR) will be the proportion of patients with a CR, PR or Stable Disease as best response under TKI treatment (cf. CRF page 36).

- Objective Response Rate (ORR) under mTOR in 2nd line post Sunitinib

ORR is defined as the percentage of patients with complete response (CR) or partial response (PR) as best response under mTOR treatment (cf. CRF page 36).

- Clinical benefice Rate (CBR) under mTOR in 2nd line post Sunitinib

The Clinical Benefit Rate (CBR) will be the proportion of patients with a CR, PR or Stable Disease as best response under mTOR treatment (cf. CRF page 36).

- Objective Response Rate (ORR) under IO in 2nd line post Sunitinib

ORR is defined as the percentage of patients with complete response (CR) or partial response (PR) as best response under IO treatment (cf. CRF page 36).

- Clinical benefice Rate (CBR) under IO in 2nd line post Sunitinib

The Clinical Benefit Rate (CBR) will be the proportion of patients with a CR, PR or Stable Disease as best response under IO treatment (cf. CRF page 36).

- Objective Response Rate (ORR) for Sunitinib received in 1st line

ORR is defined as the percentage of patients with complete response (CR) or partial response (PR) as best response under Sunitinib treatment (cf. CRF page 12 for patients included at time of Sunitinib initiation, cf. CRF page 26 for patients included at time of Axitinib initiation).

- Clinical benefice Rate (CBR) for Sunitinib received in 1st line

The Clinical Benefit Rate (CBR) will be the proportion of patients with a CR, PR or Stable Disease as best response under Sunitinib treatment (cf. CRF page 12 for patients included at time of Sunitinib initiation, cf. CRF page 26 for patients included at time of Axitinib initiation).

OS status and OS time will be calculated as detailed below:

Variable name	Definition					
OS status	Patient will not be censored for the OS analysis (OS status = 1) in the following cases:					
	1) Death reported in Long term Follow-up (cf. CRF page 36)					
	 Death reported on the Study Discontinuation form (cf. CRF page 37) 					
	In all other cases, patient will be censored for the OS analysis (OS status $= 0$).					
OS time	The overall survival time will be calculated in months as:					
(months)	 (Date of death reported in Long term Follow-up - Start date of Sunitinib + 1) / 30.44, if case n°1 described above is reported 					
	 (Date of death reported on the Study Discontinuation form - Start date of Sunitinib + 1) / 30.44, if case n°2 described above is reported 					
	Else, the overall survival time will be censored as follows:					
	 (Maximum of {All visits dates reported} - Start date of Sunitinib + 1) / 30.44 					
	Note: Start date of Sunitinib will be the one reported :					
	- at time of Sunitinib initiation visit for patients enrolled at SU initiation (cf. CRF page 11 " Therapy started with Sunitinib in 1st line on ")					
	- at time of Axitinib initiation visit for patients enrolled at AXI initiation (cf. CRF page 26 "Therapy started with Sunitinib in 1st line on")					

- Progression Free Survival (PFS) for Sunitinib received in 1st line

PFS status and PFS time will be calculated as detailed below:

Patients included at time of Sunitinib initiation (i.e. prospective group)

Variable name	Definition
PFS status	Patient will not be censored for the PFS analysis (PFS status = 1) in the following cases:
	 Tumor Assessment showing PD in at least one Sunitinib follow- up visit (cf. CRF page 12)

Variable name	Definition					
	 2) Death within 3 months after treatment discontinuation / last Tumor Assessment. Death could be reported whether on Sunitinib discontinuation page (cf. CRF page 17) or on Study Discontinuation visit (cf. CRF page 37) 					
	In all other cases, patient will be censored for the PFS analysis (PFS status $= 0$).					
	Note: the following cases should be discussed at time of DRMs:					
	- Patients with a PD not documented through a Tumor Assessment					
	- Patients with no regular Tumor Assessments (i.e. not every 3/4 months)					
PFS time	The time to disease progression will be calculated in months as:					
(months)	 (Date of first Tumor Assessment showing PD in at least one Sunitinib follow-up visit - Start date of Sunitinib + 1) / 30.44, if case n°1 described above is reported 					
	 (Date of death - Start date of Sunitinib + 1) / 30.44, if case n°2 described above is reported 					
	Else, the time to disease progression will be censored as follows:					
	 (Date of Sunitinib discontinuation - Start date of Sunitinib + 1) / 30.44 if patient discontinued Sunitinib for any reason other than PD 					
	• (Date of last follow-up visit - Start date of Sunitinib + 1) / 30.44 if patient is lost to follow-up or still under Sunitinib					
	Note; this could be adapted if necessary (to be discussed at time of DRMs)					
	Note:					
	- Start date of Sunitinib will be the one reported at time of Sunitinib initiation (cf. CRF page 11 " Therapy started with Sunitinib in 1st line on ")					
	- Sunitinib discontinuation date will be the Date of progression/intolerability or death reported at time of Sunitinib discontinuation (cf. CRF page 17)					

Patients included at time of Axitinib initiation (i.e. retrospective group)

Variable name	Definition					
PFS status	Patient will not be censored for the PFS analysis (PFS status = 1) in the following case: Sunitinib discontinued due to progression (cf. CRF page 27)					
	In all other cases, patient will be censored for the PFS analysis (PFS status $= 0$).					
PFS time	The time to disease progression will be calculated in months as:					
(months)	 (Date of progression under Sunitinib - Start date of Sunitinib + 1 / 30.44, if case described above is reported 					
	Else, the time to disease progression will be censored as follows:					
	 (Date of Sunitinib discontinuation - Start date of Sunitinib + 1) / 30.44 					
	Note:					
	- Start date of Sunitinib will be the one reported at time of Axitinib initiation visit (cf. CRF page 26 " Therapy started with Sunitinib in 1st line on ")					
	- Date of progression under Sunitinib will be the one reported on CRF page 27 (Section "Reason for discontinuation of Sunitinib", item "Progression on")					
	- Sunitinib discontinuation date will the reported on CRF page 26 (Section "Therapy with Sunitinib in first line", item "Therapy discontinuation on")					

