8.3. Variables

Variable	Role	Data source(s)
Patient demographics (year of birth, gender, height, weight)	baseline characteristics	Initiation visit
Performance status (ECOG, Karnofsky)	baseline characteristics, potential confounder	Initiation visit Follow up visit
Risk groups (MSKCC risk, Heng risk)	baseline characteristics, potential confounder	Initiation visit
Comorbidities	baseline characteristics, potential confounder	Initiation visit
Lab tests (abnormal findings – levels when abnormal)	baseline characteristics, potential confounder	Initiation visit Follow up visit
Blood Pressure measurement (Y/N, date of exam and level, antihypertensive treatment)	baseline characteristics, outcome	Initiation visit Follow up visit
Electrocardiogram (Y/N/date of exam/ abnormal findings)	baseline characteristics,	Initiation visit
Echocardiography (Y/N/date of exam/ abnormal findings, LVEF)	baseline characteristics,	Initiation visit
Tumor history (date of first diagnosis, TNM, Grade at diagnosis /at enrolment, Histology)	baseline characteristics	Initiation visit
Metastasis (date of first detection and	baseline characteristics	Initiation visit

localisation)		
Previous treatments for RCC (Surgery, radiotherapy, other / for primary tumor/ for metastasis)	baseline characteristics, potential confounder	Initiation visit
Sunitinib therapy (starting date and dose, dose change, change of schedule)	exposure	Initiation visit Follow up visit
Axitinib therapy (starting date and dose, dose titration up, dose reduction, change of schedule)	exposure, effect modifier/sub-group identifier	Initiation visit Follow up visit
Additional anti tumor treatment (name and dose)	exposure, potential confounder	Inclusion visit Follow up visit
Comedications (name of products, starting and ending dates)	exposure, potential confounder	Initiation visit Follow up visit
Sunitinib / Axitinib Progression (Y/N and date)	outcome	Initiation visit Follow up visit
Sunitinib / Axitinib Tumor Response	outcome	Initiation visit Follow up visit
Sunitinib / Axitinib Safety : AE description and AE grade (according CTCAE)	outcome	Initiation visit Follow up visit
Sunitinib / Axitinib discontinuation	outcome	Follow up visit
Axitinib QoL (FKSI-19, and MH and RE domains of SF-36)	outcome	Initiation visit Follow up visit End of treatment
Death (Y/N,date, Cause)	outcome	Follow up visit

Table 1 : variables collected during study

Detailed definitions will be included in the Statistical Analysis Plan

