6. STUDY DISCONTINUATION

Study Discontinuation
Please complete this form in case of study discontinuation during the study at any time of the study for any reason
Date of study discontinuation : / / (DD/MMYYYYY)
Reason for study discontinuation
☐ Subject did not show up again (e.g. moved away), "Lost to follow-up",
☐ Subject was enrolled in another clinical study
☐ Subject's request / withdrawal of subject's consent
□ Death
☐ Other, please specify :
If the patient is alive at study discontinuation:
Date of the last visit with the patient at the site / / (DD/MM/YYYY)
If the patient was treated with Sunitinib / Axitinib* at the previous visit :
Sunitinib /Axitinib* status at the last visit date : □ Ongoing □ Discontinued
End date / (MM/YYYY)
Reason for discontinuation
□ Progression disease Date : ᆜᆜ / ᆜᆜ / ᆜᆜ ᆜ
□ Intolerance
□ other
*: name to be selected according to the line of the treatment
In case of death 2 Voc No.
In case of death ?
Date of death
Cause tumor-related other cause
If the patient was treated with Sunitinib / Axitinib* at the previous visit:
Sunitinib / Axitinib* status at the date of death : □ Ongoing □ Discontinued End date □□ / □□□□ (MM/YYYY)
Reason for discontinuation
☐ Progressive disease Date : ☐ / ☐ / ☐ ☐ Intolerance
□ other
*: name to be selected according to the line of the treatment
. Have to be delected describing to the line of the treatment

ADONIS CRF

Subject ID:

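### For both PFS primary endpoints, the SAP's provisional default censors a progression recorded only as the dated reason for stopping axitinib, usually with no PFS time rule and with no criterion for the data review meeting

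*SAP*

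**What the plan says.** Protocol 8.1.1 (Study endpoints) and 8.7.1 define axitinib PFS and the combined SU-AXI PFS by progression or death of any cause. The verbal definitions in SAP 6.1.1 do the same. Protocol Table 1 (8.3) lists "Sunitinib / Axitinib Progression (Y/N and date" as an outcome on its own line, apart from tumour response.

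The derivation tables in SAP 6.1.1 are narrower, and they are the same for both PFS endpoints:

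- **Event, case 1:** PD on a tumour assessment at an axitinib follow-up visit (CRF page 29 in the SAP's numbering).
- **Event, case 2:** "Death within 3 months after treatment discontinuation / last Tumor Assessment", with CRF pages 35 and 37 named as the sources of the death.
- **Default:** "In all other cases, patient will be censored for the PFS analysis".
- **Censoring time, rule 1:** the axitinib stop date "if patient discontinued Axitinib for any reason other than PD".
- **Censoring time, rule 2:** the last follow-up visit, for patients lost to follow-up or still on axitinib.
- **Note:** "Patients with a PD not documented through a Tumor Assessment" is one of two groups to be discussed at the data review meeting. A further note says the time rule may be adapted there. No criterion is given.

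The CRF collects the missing information. The discontinuation block of the axitinib follow-up form (page 35) allows one stop reason, and Progression has its own full date. The Study Discontinuation form (page 37) has a section headed "If the patient was treated with Sunitinib / Axitinib* at the previous visit", which also allows progression with a date as the stop reason.

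**The concern.** A patient can be recorded as having stopped axitinib for progression, with a date, and still not be a PFS event. That sits badly with a definition that counts any progression. It also treats patients as censored at or near the moment they fail, which is informative censoring and lengthens the estimated median.

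Two of the four primary endpoints are involved. For an identifiable group, both status and time would be settled at a meeting, with the data in view and no written rule. Protocol 8.2 requires no visits and only expects assessments at approximate intervals, so progression without a recorded PD assessment is plausible. That the SAP names the group suggests its authors expected some.

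Protocol 8.5 calls the objective descriptive and SAP 4.2 plans no statistical test. What is at stake is therefore the reported median and its interval, not a test result.

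**Working it through.** **1. Trace the patient.** Stop reason Progression, dated on CRF page 35; no PD on page 29; no death in the 3-month window.

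- Case 1 fails and case 2 fails, so the default applies: status 0.
- Time rule 1 excludes stops for PD. Time rule 2 needs loss to follow-up or ongoing axitinib. Unless the patient is lost to follow-up, no time rule applies.
- If such a patient does die inside the window, the event counts, but at the death date and not at the earlier progression date.

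**2. Compare with the neighbouring SAP rules.**

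| Endpoint | Is a stop for progression, without a PD assessment, an event? |
|---|---|
| Axitinib PFS and sequence PFS (6.1.1) | No, by default |
| Prospective sunitinib PFS (6.1.2) | No, by default; same rule and same note |
| Retrospective sunitinib PFS (6.1.2) | Yes: "Sunitinib discontinued due to progression (cf. CRF page 27", at the recorded progression date |
| TTF (6.1.1) | Yes: "Axitinib discontinued due to Progression, Intolerability or Death (cf. CRF page 35", at the recorded date |

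Retrospective sunitinib PFS is the relevant contrast. TTF is meant to count stops, so it shows only that the SAP accepts the page 35 date.

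**3. Reproduce the planned precision.** Protocol 8.5 gives 5.2% at n = 350. 1.96 x sqrt(0.25/350) = 0.0524, which agrees. To convert to months, assume exponential PFS with a median of 6.5 months (the investigator-assessed figure cited in protocol sections 6 and 8.5). The slope of S(t) at the median is 0.5 x ln2/6.5 = 0.0533 per month, so the half-width is 0.052/0.0533 = 0.98 month, or 15% of the median.

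**4. Illustrate the shift.** Let f be the fraction of PFS events that are progressions and p the share of progressions recorded only as a stop reason. The documents give neither. Censoring those cases at the stop date leaves the hazard (ln2/6.5)(1 - f p), so the apparent median is 6.5/(1 - f p).

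| p | f = 0.8 | f = 0.9 | f = 0.95 |
|---|---|---|---|
| 2% | 6.61 | 6.62 | 6.63 |
| 5% | 6.77 | 6.81 | 6.82 |
| 10% | 7.07 | 7.14 | 7.18 |

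At f = 0.9 the shift is +0.12, +0.31 and +0.64 month. It equals half of the 0.98-month half-width at p of about 8% and all of it at about 14.5%.

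**5. See how far the answer depends on what is left open.** This simulation used 300,000 patients per scenario, with p = 10% and f = 0.9. It further assumed a median of 10 months from progression to death, a last assessment uniformly 0 to 2 months before the stop, and 0 to 20% independent stops for other reasons.

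| Handling of the affected patients | Median PFS (months) |
|---|---|
| Event at the stop date | 6.47-6.49 |
| Censored at the stop date | 7.10-7.12 |
| Same, with the 3-month death rule | 7.00-7.01 |
| Censored at the last assessment | 7.04-7.05 |
| Dropped for want of a time | 6.49-6.60 |

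The death-rule row depends on the assumed 10 months. Then 1 - 0.5^(3/10) = 19% of these patients die within 3 months; with 5 months it would be 1 - 0.5^(3/5) = 34%, and the shift would be smaller. The sequence endpoint was not simulated, because the documents give no sunitinib duration.

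**6. Death window.** The protocol definition has no 3-month limit. The limit's start can be read as the treatment stop or as the last assessment, and the readings differ by the time between the two. For example, a death 2 months after the stop and 3.5 months after the last assessment is an event on the first reading and censored on the second. The PFS rule names only CRF pages 35 and 37 as sources, whereas the OS rule for the sequence also uses deaths on the long-term follow-up form.

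**The case against.** The strongest reply is that the SAP has already seen this. It names the group, sends it to the data review meeting and allows the time rule to be adapted. A reader might infer that the SAP has decided to censor these patients; it has not. The censoring is a provisional default. What stands against the plan is that no criterion is written in it. Data-handling conventions planned under protocol 8.6 are not available to check.

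A reader might also infer that these patients never have a PFS time. That goes too far. A patient lost to follow-up gets the last-visit date. The exclusion of PD in the stop-date rule could also be read as meaning assessment-documented PD, in which case that rule would cover the group. The wording does not say so.

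Nor is there a clean split between axitinib and sunitinib rules. Prospective sunitinib PFS has the same assessment-only rule, and the retrospective form collects only best response and a stop reason, which partly explains its different rule. TTF is a different endpoint, so counting the stop there is not a contradiction.

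Requiring a documented assessment can be defended. The protocol leaves detailed definitions to the SAP, eligibility requires RECIST-measurable disease, and the CRF assessment section is headed RECIST. That supports keeping assessment-only PD as an analysis. It does not supply the missing time or criterion, nor does it square the default with a definition that counts any progression.

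The share may well be small. Assessment and stop reason sit on the same follow-up form, and SAP 7 makes some entries obligatory. Protocol 8.9.4 concerns how response is judged, not whether an assessment is recorded, so it is not evidence of a large share.

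**Conclusion.** The point holds for the written rule. For both PFS primary endpoints, a dated stop for progression without a PD assessment or a death in the window defaults to censored, usually with no applicable time. The only provision is a meeting with no stated criterion. This is worth fixing because, if the default is applied at the stop date, the error always lengthens the median and a larger sample does not reduce it.

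The size is not established. The figures of 6.62, 6.81 and 7.14 months rest on exponential PFS, a 6.5-month median, 90% of events being progressions, and shares that no document supplies. At 2% the shift is small beside the planned half-width of about 0.98 month. Counting these patients as events leaves the median essentially unchanged, and dropping them moves it by at most about 0.1 month in the simulation.

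On the death window, a reader might infer from the expected 2-monthly assessments that the two readings differ by at most about 2 months. The documents do not support a bound, because protocol 8.2 makes that interval approximate and requires no scans. The supported statement is that the readings differ by the time from last assessment to stop, and that the limit itself is not in the protocol definition.

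**What to change.** Before the data review meeting, amend SAP 6.1.1 for both PFS endpoints, and prospective sunitinib PFS in 6.1.2 for consistency:

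- **(a) Event.** Take the earlier of PD on a tumour assessment or discontinuation for progression at its date on the discontinuation page (for axitinib, CRF page 35; the page 37 date if recorded only there). Keep assessment-only PD as a sensitivity analysis, with stop-reason-only cases censored at the stop date. Report how many patients are affected.
- **(b) Death window.** State one start and apply it to deaths from any form, including the long-term follow-up form. Either put the 3-month limit in a protocol amendment, since protocol 8.7 says major changes to primary endpoint definitions would be reflected in one, or add a sensitivity analysis counting all deaths before new anticancer therapy.
- **(c) Remaining cases.** Give each a censoring date, including stops for other reasons. SAP 6.3.1 anticipates these, but the PFS stop date is drawn only from progression, intolerability or death dates.

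The cost is SAP wording and derivation code; the progression dates are already collected. The all-deaths sensitivity analysis also needs a day convention, because the long-term form dates the start of new drugs by month and year only. The downside of (a) is that clinical progressions without imaging enter the primary analysis, so the median may be slightly shorter. The assessment-only sensitivity analysis will show by how much.
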